##### **4.2.2 Secondary and Exploratory Outcome Variables/Endpoints (if applicable)**

The variables used to assess the secondary objectives include healthcare utilization, rates of outpatient evaluation, confirmation of outpatient assessment, new diagnoses of dementia or mild cognitive impairment (MCI), and changes in outpatient primary care.

### **5 Study Participants**

#### **5.1 Study Population**

The study will include all ED patients 65+ years in age seen in the YNHH and Northwestern Memorial Hospital EDs that receive an outpatient clinic referral for a cognitive assessment evaluation over January 2021 – December 2021.

#### **5.2 Number of Participants**

All patients 65+ years in age seen in both EDs during the study period will be screened in the ED using clinical screening for UCID.

A convenience sample of 100 hundred subjects (50 from each site) will be included for retrospective and prospective observational data via chart review and interview to evaluate rate of UCID detection in the ED, rates of referral for outpatient evaluation, rates of confirmed cognitive impairment or dementia by the outpatient evaluation, and differences across the two sites with processes, utilization, and outcome endpoints.

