#### **5.3 Eligibility Criteria**

In order to be eligible for inclusion in the study, an individual must meet all of the following criteria:

- Adults age 65 or older
- Discharged from the adult ED at YNHH or the ED at NMH

Any individual who meets any of the following criteria will be excluded from participation in this study:

- Documented or known history of dementia
- Alcohol/substance intoxication while in the ED
- Non-English or Non-Spanish speaking

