#### **6.1.1 Data Collection**

As this is a pilot study, we will gather a convenience sample of 100 participants who are eligible to be referred for outpatient cognitive assessment (50 from each site) will be evaluated. Data will be collected by telephone interview follow-up and chart review for observational characterize subjects, sites, processes, utilization, and outcome endpoints.

Research staff at both sites will contact by telephone the selected participants to conduct two focused interviews at 1-6 weeks and 3 months post-ED visit. The survey will assess the participants experiences through the process, findings of the assessment and the participants follow-up care plan. A retrospective chart review will be conducted on these participants. Trained research staff at each site will conduct chart review in the Electronic Medical Record to determine rates of:

- Healthcare utilization by the patients during the subsequent 30 days in addition to the requested outpatient cognitive assessment, inpatient hospitalizations, and/or ED revisits up to 6 months prior to the current ED visit

- Referral and completion of outpatient cognitive assessment
- New outpatient diagnoses of Alzheimer's Diseases or Related Dementia diagnoses or mild cognitive impairment
- Documentation of Outpatient Cognitive Assessment communication with the patients' primary care providers or other consults of results and recommendations for brain health treatment and management.

Trained research assistants will review the medical records of potentially eligible participants seen in the ED during the study period to assess clinician compliance and acceptance of screening intervention.

Data for this study will be collected, recorded and stored using Redcap (Research Electronic Data Capture). Redcap is a secure, web application designed to support data capture for research studies. Data from any paper study forms will be entered into Redcap and then stored in locked file cabinets restricted to the study team. Data coordination, data management, and database design will occur within the Yale School of Medicine's Program on Aging. See Table 1 for data points that will be collected.

Retrospective chart review will be conducted on a subset of 100 patients as part of study enrollment: We will collect data on a subset of patients meeting inclusion criteria (50 from each site, for a total of 100 subjects).

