## **8.4 Access to Source**

For identification of eligible participants for recruitment and enrollment, research staff will maintain a password protected screening log to track patients who are referred from the ED

for outpatient cognitive assessment. Participants enrolled will be assigned generated participant identification codes to facilitate the de-identification process.

Data will be collected and merged from clinical and administrative reports and chart review by trained research staff into a single Redcap database.

As this use of administrative and retrospective clinical data and chart review are only minimal risk a waiver of signed consent will be requested.

Source data are all information, original records of clinical findings, observations, or other necessary activities in a research study. Source data are contained in source documents. Research staff at the local site will access the following source documents to extract data for medical record abstraction including: ED records, inpatient records, readmission records, consultations, outpatient records (clinical and office charts), medication administration records and other reports.

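### Sections 5.1 and 8.4 make the 100 subjects referred patients and 5.3 does not; under the first rule their referral rate is 100% by selection, and no analysis section assigns the detection or referral rate to a wider population

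*Combined protocol and SAP*

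**What the plan says.** **Who the 100 are**

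- Section 5.1 limits the population to patients aged 65+ seen in the two "EDs that receive an outpatient clinic referral for a cognitive assessment evaluation".
- Section 8.4: "For identification of eligible participants for recruitment and enrollment", staff keep a "password protected screening log to track patients who are referred from the ED".
- Synopsis, Study Population: community-dwelling ED patients aged 65 or over at the two hospitals. No referral is required.
- Section 5.3: age 65 or over and "Discharged from the adult ED at YNHH or the ED at NMH", with three exclusions. No referral is required.
- Section 5.5: staff check basic inclusion and exclusion criteria in the EMR and enrol those who meet them. No referral is mentioned.
- Section 6.1.1 opens with a "convenience sample of 100 participants who are eligible to be referred for outpatient cognitive assessment", which can be read either way. It closes with "We will collect data on a subset of patients meeting inclusion criteria (50 from each site, for a total of 100 subjects".
- Section 5.4 refers to daily lists and a site recruitment policy without saying who is listed.

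**What is taken from the 100**

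- Section 5.2 includes them "to evaluate rate of UCID detection in the ED, rates of referral for outpatient evaluation", and to compare the two sites.
- Synopsis, Number of Participants: screening and referral rates.
- Section 6.1.1: chart review of these participants determines, among other things, the rates of referral and of completed evaluation.

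**Endpoints and analysis**

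- Section 4.2.1 defines screening and detection over every ED patient aged 65 or over, and referral over those found at risk. Both are primary there.
- The synopsis lists referral as secondary, among screened patients.
- Section 7 labels discharged patients 65+ as a denominator, in a comparison of demographic and clinical characteristics with referred patients.
- Section 7.2 lists a proportion at risk and a number referred, without naming the data source.
- Section 7.3 names the overall eligible subjects and the subset of 100, and ties no rate to either.

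**The concern.** A referral rate cannot be estimated in people chosen because they were referred. If the entry rule in 5.1 and 8.4 is applied and the referral rate is then computed as 5.2, the synopsis and 6.1.1 describe, the result is settled before any data are collected. EDs that missed most at-risk patients would report the same figure as EDs that missed none.

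Referral is a primary endpoint in 4.2.1, and UCID detection is primary in both the synopsis and 4.2.1. Sections 4.2 and 7.1 say the pilot will inform the effect sizes and sample size of the later multicentre trial. A referral rate fixed by selection would enter that planning as if it had been observed.

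**Working it through.** **1. The sample size.** 2 sites × 50 = 100, as stated. No expected rate, precision target or power is given, so nothing further can be reproduced.

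**2. Referral if 5.1 and 8.4 govern.** Let r be the true referral rate in the chosen denominator. In a sample restricted to referred patients:

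- P(referred | selected because referred) = 1, for any r above 0.
- Overall: 100/100 = 100%.
- Each site: 50/50 = 100%.
- Site difference: 100% − 100% = 0 points, however far apart the true site rates are.

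An exact 95% interval could still be printed. When all n are positive, the Clopper-Pearson lower limit is 0.025^(1/n): 0.025^(1/100) = 96.4% and 0.025^(1/50) = 92.9%. Intervals of 96.4% to 100% and 92.9% to 100% would look precise but would carry no information about r.

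**3. Detection if 5.1 and 8.4 govern.** Section 6.1 has referral follow clinician suspicion, so a referred sample is enriched for detected patients and the rate is inflated. The size is open. Section 6.1 lets the clinician refer on suspicion whatever the patient or caregiver answers, and the data table in 6.1.1 has a delirium screen and a memory item but no field for clinician suspicion. If a share s of referred patients has no positive recorded field, detection counted from those fields is 1 − s. An assumed s of 5% to 10% would give 95% to 90%, but the documents neither state s nor bound it.

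**4. Both rates if 5.3 governs.** Neither is fixed. The 100 would be discharged patients who could be reached and who agreed by telephone (or by proxy), taken as a convenience sample. The 4.2.1 population is every ED patient aged 65 or over. Admitted patients, patients not reached and patients who declined are missing from the 100. The documents give no ED volume, at-risk rate or referral rate, so this bias cannot be sized.

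**5. Does another section assign the rates to wider data?**

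| Section | Wider data named | Stated use |
|---|---|---|
| 5.2, first sentence | All 65+ patients in both EDs | Clinical screening |
| 5.5 | EMR records under a full waiver | Comparison with enrolled patients |
| 6.1.1 | Records of potentially eligible patients | Clinician compliance and acceptance |
| 7 | All discharged patients 65+ | Comparison of characteristics |
| 7.2 | Not named | Proportion at risk, number referred |
| 7.3 | Overall eligible subjects | Descriptive comparison |
| 8.4, 9.3 | Administrative reports, monthly ED metrics | Merged database, quality review |

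The 6.1.1 review of patients "seen in the ED during the study period to assess clinician compliance and acceptance of screening intervention" could supply a screening rate. No row assigns the detection or referral rate to the wider population.

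**The case against.** The best reply is that the sponsor plainly means the wider population. Section 5.3 is the formal eligibility list, and the synopsis and 5.5 agree with it. The data table collects whether a referral was requested, a field with little purpose if everyone was referred. Section 7 sets all discharged patients 65+ against those referred, and the two group sizes would give an overall referral proportion directly. Section 7.3 uses the overall eligible group. The study is also a feasibility pilot that tests no hypothesis about effect.

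Much of this stands. It shows that the 5.1 and 8.4 rule is not the only reading, and that the data for a sound estimate are within reach. It does not remove the conflict: 5.1 and 8.4 still say referred patients, and three places take the referral rate from the 100. The section 7 proportion could be derived, but the plan does not say that it is the endpoint. Its base of discharged patients also differs from both referral denominators, at-risk patients in 4.2.1 and screened patients in the synopsis. Pilot status does not help, because producing usable rates is the pilot's purpose.

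A reader might also infer that, under 5.1 and 8.4, detection must come out near 100% and the no-deficit category must be almost empty. The documents do not support that. Referral may rest on suspicion that no recorded field shows, so only the referral figure follows by logic.

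**Conclusion.** The concern holds in a limited form. The entry rule for the 100 is contradictory. Under 5.1 and 8.4 the referral rate is 100/100, 50/50 at each site, with a site difference of 0, all by selection. Detection is inflated by an amount that cannot be fixed from the documents. Under 5.3 no rate is fixed, but the sample does not represent the population of 4.2.1. Under either rule, no analysis section says that detection and referral are to be computed from the wider population.

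The 100% figure assumes only that 5.1 and 8.4 are applied as written. It would be too strong to conclude that the whole pilot is uninformative. Completed evaluations, diagnoses after referral and the review of screening compliance are not fixed by this selection, and sections 7 and 7.3 show that the plan is not confined to the 100. The point still needs correction before analysis, because it touches primary endpoints and enrolling more referred patients would not repair it.

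**What to change.** 1. Reconcile the synopsis, 5.1, 5.3, 6.1.1 and 8.4 to one entry rule for the 100.
2. In the synopsis, 5.2 and 7.2, state that screening, detection and referral rates are calculated by site from the EMR records of all ED patients 65+ sought under the full waiver in 5.5, and not from the 100. Count referrals from EMR consult requests plus the referral log, because 6.1 also allows referral by e-mail.
3. Report referral both among screened patients (synopsis) and among at-risk patients (4.2.1). State whether the rate denominator is all ED patients 65+ or only those discharged.
4. Use the 100 for interviews and post-referral outcomes: scheduling, completion, diagnosis and communication with primary care. If the entry rule does not require referral, the denominator for those outcomes is the referred patients among the 100.
5. Extend the purpose of the 5.5 waiver from comparison with enrolled patients to calculation of these rates.

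The cost is extraction of a few fields for all 65+ visits at both EDs (volume not stated, so the workload cannot be sized here), linkage to the referral log, and an IRB wording update. No additional patients are needed.

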#### **5.3 Eligibility Criteria**

In order to be eligible for inclusion in the study, an individual must meet all of the following criteria:

- Adults age 65 or older
- Discharged from the adult ED at YNHH or the ED at NMH

Any individual who meets any of the following criteria will be excluded from participation in this study:

- Documented or known history of dementia
- Alcohol/substance intoxication while in the ED
- Non-English or Non-Spanish speaking

#### **5.4 Recruitment Procedures**

Potential study participants will receive an informational sheet about the study stating that they are eligible to participate, either at discharge from the ED or by letter(paper or electronic through my chart). If given informational sheet while in the ED, research staff will ask for permission to contact by phone. The sheet will notify them that research staff may call them to participate but that they have the right to refuse to participate. They will also be provided with a mechanism to opt-out prior to receiving a call soliciting participation. Research staff will receive daily lists of potential study subjects.

Potential study participants will be identified at each site based on the site recruitment policy. They will be consented by study staff over the telephone and provided the required information about the study and allowed to ask questions before, during and after assent. They will be made aware that they can stop participating at any time and that such a choice will not impact their ability to seek care at the study site. Verbal consent time, date and initials of the research assistant collecting verbal consent will be documented in a case report form.

It is possible that the study PI's ([name] and [name]) may be providing or have a history of providing care for study participants, given their role as attendings in the ED. As assent to participate will be provided after ED discharge, no undue influence is expected to impact the choice to participate in the study.

## **5.5 Consent/Assent Procedures/HIPAA Authorization**

A partial waiver of HIPPA Authorization and waiver of written informed consent will be sought for recruitment and screening of patients in the ED. purposes A convenience sample of total of 100 eligible subjects will be contacted by telephone for follow-up and informed telephone assent with a waiver of written consent to participate in telephone surveys and medical record review. We will screen for basic inclusion and exclusion criteria via the electronic medical record (EMR). These waivers of HIPAA authorization and written informed consent for recruitment/screening purposes will lessen burden on patients and families (since we only intend to enroll patients who meet basic inclusion criteria), and still allow us to accurately report the number and characteristics of screened patients.

A full waiver of HIPPA Authorization is being sought for all the ED patient (EMR)records over 65 years of age during the study time period to compare with the enrolled population.

These waivers are being sought as the study is of minimal risk and for restrictions in place because of COVID.

Trained research staff will contact eligible participants by telephone approximately at 1-6 weeks and again at 3 months after their ED visit. The study will be explained to the potential participant, and any questions will be discussed. If the study personnel have concerns over the patient's capacity for informed decision making, the patient's capacity to consent will be assessed through performance of the University of California San Diego Brief Assessment of Capacity to Consent. If the patient is determined, based on a score of <10 on the capacity of assessment, to not able to make an informed decision, a proxy or legally authorized representative will be sought for consent. If the patient regains decision-making capacity during the course of the study (for example, if delirium was present at enrollment but subsequently resolves), then consent will be obtained from the patient. If the patient then refuses to consent or withdraws consent given by the proxy, the patient will be disenrolled from the study.

We will enroll Spanish-speaking subjects in addition to English-speaking subjects. We have research personnel with years of experience in patient recruitment and enrollment who are fluent in Spanish. Only these personnel will contact Spanish-speaking patients for enrollment and consent. The translated consent form and recruitment letters will be submitted to the IRB for approval prior to use.

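### Sections 5.1, 5.2, 5.3 and 6.1.1 give conflicting bases for the detection and referral rates, and no planned analysis names a follow-up outcome for referred patients who are not enrolled

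*Combined protocol and SAP*

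**What the plan says.** **Who the 100 are.** Section 5.2 includes a convenience sample of 100, 50 per site, "to evaluate rate of UCID detection in the ED, rates of referral for outpatient evaluation", as well as confirmed impairment and site differences. Section 5.5 says "A convenience sample of total of 100 eligible subjects will be contacted by telephone for follow-up and informed telephone assent". Section 5.4 adds an opt-out before the call and says "Potential study participants will be identified at each site based on the site recruitment policy". On timing, section 5.5 says "Trained research staff will contact eligible participants by telephone approximately at 1-6 weeks and again at 3 months after their ED visit".

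**Who the population is.** Section 5.1 takes ED patients aged 65+ who receive a referral for outpatient cognitive evaluation. Section 5.3 asks for age 65+ and ED discharge, with three exclusions and no referral criterion. Section 6.1.1 describes the 100 as eligible for referral.

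**What the rates are based on.** Section 4.2.1 bases detection on all older ED patients and successful referral on those found at risk, and treats both as primary. The synopsis lists referral as secondary and bases referral and completion on screened patients. Section 7 labels all discharged patients aged 65+ as the denominator.

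**Where follow-up outcomes come from.** Section 6.1.1 says "A retrospective chart review will be conducted on these participants". The items listed there include completion of the outpatient assessment, new diagnoses and "Healthcare utilization by the patients during the subsequent 30 days".

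**Wider data.** Section 5.5 seeks a waiver for "all the ED patient (EMR)records over 65 years of age during the study time period to compare with the enrolled population". Section 6.1.1 says "Trained research assistants will review the medical records of potentially eligible participants seen in the ED during the study period to assess clinician compliance". Section 8.4 describes a screening log of referred patients, and section 8.3 an outpatient-attendance tracker within the log.

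**The concern.** There are two linked problems.

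First, the sections define different studies. A sample made up only of referred patients cannot yield a referral rate. It cannot yield a detection rate either, because under section 6.1 referral follows clinical suspicion. A sample of any eligible discharged patients can yield both, but may contain few referred patients in whom to observe completion or diagnosis.

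Second, the 100 enter only if they are reached and agree by telephone after the visit. Two routes by which outcome could affect entry are visible in the text. The first call may come as late as week 6 (42 days), after the 30-day utilization window has closed, so an event in that window can affect who is reached. Patients whose capacity is in doubt need an assessment and possibly a proxy, so entry may depend on cognition.

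Section 7.2 says the study's product is estimates for a larger pragmatic evaluation. A reader of the results could not tell which base a rate used, or whether a completion rate describes the referral pathway or the people who answered the telephone.

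**Working it through.** **The plan's own figure.** 50 + 50 = 100. Section 7.1 gives no rate, precision target or power, so there is nothing further to reproduce. Every rate below is an assumption.

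**1. Effect of the base.**

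- Section 5.1 governs: all 100 are referred, so the referral rate is 100/100 = 100% whatever the clinicians do.
- Section 5.3 governs: expected number referred = 100 × a × r, where a is the share at risk and r is the share of those who are referred. With a from 10% to 30% and r from 30% to 80%, this runs from 100 × 0.10 × 0.30 = 3 to 100 × 0.30 × 0.80 = 24. If half complete, 1.5 to 12 are evaluated.
- Even with 24 referred, the 95% half-width at 50% completion is 1.96 × √(0.25/24) = 20.0 points.
- The same 50% completion among referred patients is 1.5% to 12% of all eligible patients.

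**2. Coverage of the planned comparisons.**

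| Section | Groups | Variables named |
|---|---|---|
| 5.5 | All older ED records vs enrolled | No outcome named |
| 6.1.1 | Potentially eligible patients | Clinician compliance with and acceptance of screening |
| 7 | All discharged 65+ vs referred | Demographic and clinical characteristics |
| 7.3 | Overall eligible vs the 100 | None named |

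None names completion, new diagnosis or utilization for referred, non-enrolled patients.

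**3. Possible shift from selection.** Let p be the true rate and k the chance of enrolment for patients with the outcome relative to those without (assumed). Observed rate = pk / (pk + 1 − p).

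| k | p = 40% (completion) | Shift | p = 20% (utilization) | Shift |
|---|---|---|---|---|
| 0.5 | 0.20/0.80 = 25.0% | −15.0 | 0.10/0.90 = 11.1% | −8.9 |
| 0.75 | 0.30/0.90 = 33.3% | −6.7 | 0.15/0.95 = 15.8% | −4.2 |
| 1 | 40.0% | 0 | 20.0% | 0 |
| 1.25 | 0.50/1.10 = 45.5% | +5.5 | 0.25/1.05 = 23.8% | +3.8 |
| 1.5 | 0.60/1.20 = 50.0% | +10.0 | 0.30/1.10 = 27.3% | +7.3 |

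**4. Sampling error for comparison.** Half-width = 1.96 × √(p(1−p)/n).

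- p = 40%: 9.6 points at n = 100 and 13.6 at n = 50.
- p = 20%: 7.8 and 11.1 points.
- Site difference at p = 40%: 1.96 × √(2 × 0.24/50) = 19.2 points. With equal true rates, opposite selection by site gives a false difference of 50.0 − 33.3 = 16.7 points (k = 1.5 vs 0.75) or 50.0 − 25.0 = 25.0 points (k = 1.5 vs 0.5).

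Depending on k, the shift falls inside or outside sampling error, both pooled and by site.

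**5. What the missing outcome leaves open.** Let f be the enrolled share of referred patients. If f = 50% and 60% of the enrolled complete, completion in all referred patients lies between 0.5 × 0.6 = 30% and 30% + 50% = 80%.

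**The case against.** The strongest reply has four parts.

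- **This is a declared pilot.** Section 4.2 says no hypotheses are tested, and section 6.1.1 justifies the convenience sample on that ground. This stands: a convenience sample is not an error here, and the follow-up rates are secondary.
- **The population sections can be read together.** Sections 5.1 and 5.3 could be a population plus further criteria, and section 8.4 supports this by identifying participants from a log of referred patients. On that reading, the overall eligible subjects in section 7.3 are the referred patients, so 7.3 does compare referred patients with the 100. This partly stands. But 7.3 still names no variable, and the same reading makes the referral rate assigned to the 100 in section 5.2 equal to 100%.
- **Selection would partly show.** Section 5.5 compares older ED patients' records with the enrolled, so baseline differences may be seen. Proxy consent and Spanish-speaking staff reduce two routes of selection. Section 7.7 treats missing data as informative. All this stands, but matching baseline characteristics do not show that completion or utilization also match.
- **Section 7.2 does not confine its counts to the 100.** Read with the synopsis, it makes evaluated patients the evident base for diagnosis. That stands, and diagnosis is not a rate without a denominator. Section 7.2 still does not name completion for non-enrolled patients, and section 6.1.1 assigns its collection to the participants.

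A reader might infer that the plan has no data on non-enrolled patients. The documents do not support this: the waiver sought in section 5.5 and the log and tracker in sections 8.3 and 8.4 could supply attendance. They are simply not tied to an analysis, and whether the tracker covers all referred patients is not stated.

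**Conclusion.** The point holds in two parts of different strength. The conflict over bases is plain on the text: following sections 5.1 and 5.2 as written gives an uninformative referral rate and no usable detection rate from the 100. Section 4.2.1 already names bases outside the 100 for both.

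The selection part is a gap in the analysis plan. Follow-up outcomes are assigned to people who were reached and agreed, and no planned comparison names those outcomes for the other referred patients.

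A reader might go further and infer that the follow-up rates are biased, or that bias must outweigh sampling error. The documents do not support either. They give no completion, utilization, response or referral figures, so size and direction are unknown. At an assumed 40% completion and k from 0.5 to 1.5, the shift runs from -15.0 to +10.0 points against half-widths of 9.6 (n=100) and 13.6 (n=50). These figures take all 100 as enrolled and analysed. A confidence interval from the sample would not reveal such a shift, and a larger convenience sample would not remove it unless it raised the enrolled share.

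Both parts should be corrected. Confidence is medium, and neither part undermines the study as a pilot.

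**What to change.** 1. **State one base per rate**, reconciling the synopsis with sections 4.2.1, 5.1, 5.2, 5.3, 6.1.1 and 7.
   - Detection: all older ED patients screened.
   - Primary referral rate: patients found at risk, as in section 4.2.1. Report the synopsis rate among all screened patients separately.
   - Completion: all screened patients, as the synopsis states, and additionally all referred patients.
   - Diagnosis: evaluated patients.
   - Utilization: a named cohort.
   - Remove detection and referral rates from the purposes of the 100 in section 5.2.

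2. **Use the log and tracker.** In sections 6.1.1 and 7.2, add that completion of the outpatient evaluation will be reported for all referred patients on the screening log, using the attendance tracker, by site, and descriptively for enrolled and non-enrolled patients with 95% confidence intervals. Make this subject to IRB confirmation that the section 5.5 waiver covers it, excluding opt-outs as required. State in section 8.3 that the tracker covers all referred patients.

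**Cost.** Item 1 costs only text. Item 2 needs IRB confirmation, because section 8.4 gives the log's purpose as recruitment and enrollment, and some extra abstraction, modest for completion alone. The number of referred patients is not given. The side-by-side comparison will be imprecise: at 40% completion, the half-width is 1.96 × √(0.24 × (1/100 + 1/m)), which is 13.6 points for m = 100 non-enrolled and 11.1 for m = 300 (m assumed).

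As a suggestion only, log approaches, refusals and non-contacts. Calling in consecutive or random order is optional: the site recruitment policy may already set call order, and ordered calling would not remove bias from non-contact or refusal.
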